11.11 Return to Menses

The time to return to menses for each month following IUS removal for those women who are using non-hormonal contraceptive methods or no contraception following IUS discontinuation will be summarized by treatment group. Time to event will be calculated as the date of menstruation minus the date of removal plus one. Subjects who do not have a return of menstruation will be censored at the date of diagnosis for secondary amenorrhea and failure time will be calculated as the date of diagnosis for secondary amenorrhea minus the date of removal plus one.

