- Removal of IUS, if not already expelled or removed (at an outside location)
- Retain all removed or expelled IUSs (when possible) per the Study Reference Manual
- Contraceptive counseling
 - Immediate initiation of another method in the office when possible
 - Request to use this method or be abstinent for at least one week to avoid conception within 7 days after IUS discontinuation
- Schedule next appointment

6.7 30-Day Safety Follow-Up

All subjects must have a safety follow-up visit between 30 and 43 days after the Treatment

Completion/Early Discontinuation Visit (except those made lost to follow up or who withdrew consent per section 7.18). If the subject contacts the office with an expulsion that was 30 or more days ago, this visit may be combined with the Early Discontinuation visit.

- Review of adverse events (note: all adverse events occurring within 30 days of IUS discontinuation should be reported on the appropriate adverse event CRF)
- Review of concomitant medications used up to 30 days of IUS discontinuation
- Menstrual history if not using a hormonal method of contraception
- High sensitivity urine pregnancy test (if positive, see Sections 7.4 and 7.5)
- Weight and blood pressure
- Additional contraceptive counseling if needed
- Review with subject that continued telephone or clinic follow-up (as appropriate) is indicated for the following:
 - an ongoing IUS-related adverse event at study discontinuation should be followed monthly until the adverse event resolves or has stabilized
 - any subject electing to use a non-hormonal contraceptive method or no contraception (including those desiring pregnancy) will be followed monthly for up to 3 months after IUS removal/expulsion for return of menses. Any woman who does not menstruate within 3 months following IUS discontinuation will be referred for appropriate evaluation and continue to be followed monthly until menses has occurred or a diagnosis for the cause of the secondary amenorrhea has been established
- Those women desiring a pregnancy after IUS discontinuation will be contacted every three months from their Treatment Completion/Early Discontinuation Visit up to one year to record return to fertility.
 - Once a pregnancy is reported no further follow-up contact is required.
 - Women who do not become pregnant and change their intention before completing a full 12 months of follow-up will be discontinued from the study and not be included in the return to fertility cohort.

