Dysmenorrhea (none, mild, moderate, or severe) will be summarized by the number and percentage of days with a particular pattern during each 84 and 90 day interval after enrollment through Month 24. After Month 24 dysmenorrhea will be summarized from the Adverse Events CRF. In addition, dysmenorrhea changes from baseline will be summarized using shift tables. Baseline dysmenorrhea is recorded on the Menstrual History CRF based on menstrual characteristics when not using hormonal contraception.

- **Adverse Events**

The number and percentage of subjects with each adverse event and serious adverse event will be presented by MedDRA system organ class, preferred term, and treatment group. Summaries will also be presented by relationship to the type of IUS or IUS insertion or removal procedure and the severity of the adverse event. All adverse events will be summarized with special attention to those events that may be related to an IUS, including:

- Difficult insertion or removal procedure;
- Perforation of the uterus;
- Dysmenorrhea;
- Low abdominal pain (not classified as dysmenorrhea);
- Uterine infection (including PID); and
- Other urogenital infections

- **Pregnancy Outcomes**

Pregnancy outcomes will be summarized by treatment group using the MITT population as well as listed by subject.

- **Fertility Rates**

Those women desiring pregnancy after leaving the study will be contacted every three months up to one year after IUS discontinuation to record any pregnancy. Kaplan-Meier methods will be used to estimate the probability of pregnancy over time.

- **Menses After IUS Discontinuation**

Those women who elect to use a non-hormonal contraceptive method or no contraception (including those desiring pregnancy) will be followed monthly for up to 3 months after IUS removal/expulsion for the occurrence of menses following IUS discontinuation.

Women who do not menstruate within 3 months following IUS discontinuation will be referred for appropriate evaluation and continue to be followed monthly until menses has occurred or a diagnosis for the cause of the secondary amenorrhea has been established.

Kaplan-Meier methods will be used to estimate the probability of the return of menses over time.

- **Plasma Levonorgestrel Levels**

- Levels over the lifespan of IUS use

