5.3 Handling of Dropouts or Missing Data

Unless otherwise specified, missing data will not be imputed. Subjects who drop out will not be replaced and all available data will be used.

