5.3.4 Missing Concomitant Medication Start and Stop Dates

For concomitant medications (CM), the following rules for imputing values for missing start dates are used:

- If the CM start date field includes a SAS missing value or is completely missing, the start date is set to the IUS insertion attempt date.
- If the CM start date field is missing day only, set it equal to the first day of the recorded month and year.
- If the CM start date field is missing day and month only, set it equal to the first day of January of the recorded year.
- If the CM stop date field includes a SAS missing value or is completely missing, the stop date is set to the last date of known product use.
- If the CM stop date field is missing day only, set it equal to the 15th day of the recorded month and year
- If the CM stop date field is missing day and month only, set it equal to the 31st day of December of the recorded year.
- If the CM stop date field is missing month only, set it equal to December of the recorded year
- Any imputed CM stop date that is before the insertion attempt date implies the CM was a Pre-Trial Medication. Any medication started on or after the insertion attempt date or any medication started before insertion but ending on or before the last known date of product use is a Concomitant Medication.

5.3.5 Missing Dates for Other Events, Including Return to Menses, Return to Fertility, Pap Tests, Date of IUS Expulsion/Removal, and Reported Pregnancies

For missing dates of other events, any date that is completely missing or contains the year only will be set to the date of the subject's last clinic visit. If a month and year are recorded but the day is unknown, the day will be set to the first day of the month. If this

results in an imputed date that is earlier than the last clinic visit, the date will be set to the date of the last clinic visit.

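### The return-to-menses rule censors women at diagnosis of secondary amenorrhea and gives other non-returners no time, so the Kaplan-Meier estimate can exceed the proportion observed to return

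*SAP*

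**What the plan says.** Return of menses after discontinuation is a secondary objective in both documents (section 2.2 of each). Protocol 9.8 describes the follow-up: women on a non-hormonal method or none "will be followed monthly for up to 3 months after IUS removal/expulsion for the occurrence of menses following IUS discontinuation". Those without menses by then are referred and "continue to be followed monthly until menses has occurred or a diagnosis for the cause of the secondary amenorrhea has been established" (Protocol 6.7 and 9.8). Protocol 9.8 also names the estimator: "Kaplan-Meier methods will be used to estimate the probability of the return of menses over time".

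SAP 11.11 asks for a monthly summary by treatment group and names no estimator. For women who return, "Time to event will be calculated as the date of menstruation minus the date of removal plus one". For all others the rule is: "Subjects who do not have a return of menstruation will be censored at the date of diagnosis for secondary amenorrhea". Such a woman's time is then counted in days from removal to that diagnosis, adding one. No other censoring date is given.

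Two general rules bear on the gap. SAP 5.3 states: "Unless otherwise specified, missing data will not be imputed". SAP 5.3.5, whose heading lists return to menses, replaces an event date that is wholly absent, or known only to the year, with that of the woman's latest clinic visit.

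**The concern.** There are two separate weaknesses.

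- **Censoring depends on the outcome.** A woman reaches a diagnosis because menses has not returned. Kaplan-Meier censoring assumes that she would go on to resume at the rate of women still under follow-up. That is hard to defend where the cause is lasting, such as menopause. Safety analyses use the Safety population regardless of age (SAP 6 and 11). Women enrolled at 36 to 45 who complete 96 months of use would be about 44 to 53 at removal (36 + 8 and 45 + 8).
- **Some women have no time.** Without a diagnosis date the SAP formula cannot be evaluated. One programmer might drop such women and another might censor them at last contact, with different results. The neighbouring analyses avoid this: SAP 11.9 censors at last contact and SAP 11.10 at 12 months.

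At stake is the summary of how many women resume menses after long use. The women whom the rule treats most favourably, or leaves out, are those the outcome is meant to detect.

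**Working it through.** The documents give no sample size, event count or rate for this outcome, so there is no planned figure to reproduce. All counts below are assumptions.

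**Formulas.** Kaplan-Meier: S(t) is the product of (1 − d/n) over event times, and the estimate of return is 1 − S(t). It reaches 100% exactly when the largest observed time is a return. Cumulative incidence: at each time F rises by S × d1/n, and S is then multiplied by 1 − (d1 + d2)/n, where d1 counts returns and d2 counts diagnoses.

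**Example 1.** 100 women: 45, 30 and 15 return in months 1, 2 and 3; 5 are diagnosed at month 4; 5 return at month 5.

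| Month | At risk | Returns | Diagnosed | Kaplan-Meier under SAP rule | Cumulative incidence |
|---|---|---|---|---|---|
| 1 | 100 | 45 | 0 | 45% | 45% |
| 2 | 55 | 30 | 0 | 75% | 75% |
| 3 | 25 | 15 | 0 | 90% | 90% |
| 4 | 10 | 0 | 5 | 90% | 90% |
| 5 | 5 | 5 | 0 | 100% | 95% |

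After month 3, S = 0.10. Under the SAP rule the five diagnosed women leave without changing S; then 5 of 5 return and S = 0. With diagnosis as a competing event, S falls to 0.10 × (1 − 5/10) = 0.05, and F = 0.90 + 0.05 × 5/5 = 0.95, which matches 95/100 observed. The two methods agree through month 4.

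**Example 2.** 100 women: 91 return and 9 do not. Ninety returns fall on days 10 to 88.

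- A: last return on day 150; 5 women diagnosed on days 100 to 120; 4 without a diagnosis.
- B: as A, but last return on day 90.
- C: last return on day 90; all 9 non-returners without a diagnosis.

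| Pattern | SAP rule, undated women dropped | Kaplan-Meier, undated censored day 35 | Kaplan-Meier, undated censored day 91 | Cumulative incidence, undated censored day 35 | Cumulative incidence, undated censored day 91 |
|---|---|---|---|---|---|
| A | 100% | 100% | 100% | 94.7% | 91.7% |
| B | 94.8% | 94.7% | 91.0% | 94.7% | 91.0% |
| C | 100% | 100% | 91.0% | 100% | 91.0% |

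Some cells can be checked by hand. B under the SAP rule is 91/96 = 94.8%. C is 91/91 = 100%. A with cumulative incidence and day-91 censoring is 0.90 + 0.10 × 1/6 = 91.7%.

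Three things follow.

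1. In A, diagnosis-censoring takes the curve to 100% even when the undated women have a censoring date.
2. In B, every return precedes every diagnosis and the curve stays below 100%. Its excess over 91% comes only from how the undated women are handled.
3. Dropping undated women already matters by month 3. In A the estimate on day 88 is 90/96 = 93.75%, against 90/100 observed. In C with early loss, last-contact censoring leaves the estimate at 100%, so no estimator replaces the observed counts.

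**The case against.** The strongest reply is that routine follow-up for menses lasts 3 months and that referral, and so diagnosis, comes afterwards. Diagnosis-censoring then leaves the month-3 figure alone, as example 1 shows. This stands, and it confines that part of the problem mainly to the later tail. It does not cover women without a date, who can be missing from any month.

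Second, a reader might infer that the curve will reach 100%, or that the rule always inflates the result. The documents do not support that. Reaching 100% requires a return after the last diagnosis, or the loss of undated women from the risk set; pattern B stays at 94.8%.

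Third, the protocol asks for a diagnosis of the cause, and a cause may be reversible. Required follow-up for menses stops there, so later return is unknown. The 95% in example 1 is therefore an observed proportion, not a known truth, and the competing-event estimate answers a specific question: the probability that menses is seen to return before a diagnosis closes follow-up. That still describes what was observed without assuming later recovery.

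Fourth, SAP 5.3 says that all available data will be used, and SAP 5.3.5 supplies dates, so exclusion of undated women is only one reading. That is fair, but neither rule sets a censoring time. SAP 5.3.5 dates events that occurred; applied to the blank menses date of a non-returner, it could create a false return at the last clinic visit.

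Finally, a reader might infer that persistent amenorrhea would be concealed altogether. It would not: SAP 5.1 provides subject-level listings, and these women are referred and followed individually. The weakness is in the summary estimate.

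**Conclusion.** The point holds as a defect in the SAP 11.11 rule. Censoring depends on the outcome for diagnosed women, and the time is undefined for non-returners without a diagnosis. The estimated probability of return can exceed the observed proportion: by 5 percentage points in example 1, and by 3.8 to 9 points under the SAP rule in example 2 (94.8% to 100%, against 91%). These sizes rest wholly on assumed counts and timings. The actual size depends on how many women are diagnosed, how many are undated, and whether any return comes late.

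An estimate above the observed proportion is not wrong in itself: censoring at last contact is reasonable if loss is unrelated to return. The objection is to applying that assumption to women diagnosed because they have not returned, and to leaving undated women to the programmer's choice.

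The outcome is a descriptive secondary one. The Pearl Index is untouched, and the correction is worth making because it is cheap.

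**What to change.** Amend SAP 11.11 as follows:

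1. Estimate the cumulative incidence of return of menses (Aalen-Johansen), with diagnosed amenorrhea as a competing event.
2. Censor non-returners without a diagnosis at last contact, or at the start of a hormonal method where that date is recorded. Last contact must be the fallback, because concomitant-medication review covers only the 30 days after discontinuation (Protocol 5.6 and 6.7). Report pregnancy before first menses separately; counting it as return would redefine a menses endpoint, and fertility has its own analysis in SAP 11.10.
3. State that the date imputation in SAP 5.3.5 does not apply to women with no return of menses.
4. Report the observed number and percentage returned by 3 months, and the number never observed to return, with denominators.

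The cost is SAP wording and minor programming with a standard procedure, with no change to study conduct. The reported return rate may be slightly lower.

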11.12 Pelvic and Breast Examinations

Any abnormal pelvic or breast findings will be included in the adverse event reporting.

11.13 Clinical Laboratory Evaluation

11.13.1 Hemoglobin

Hemoglobin will be summarized using descriptive statistics at Baseline, Month 12, Month 60 and the Final Visit. Final Visit is defined as either the early discontinuation or study treatment completion visit. Baseline is defined as the last non-missing value prior to IUS insertion. However, if a baseline value is not obtained due to protocol deviation or laboratory error, a Month 1 visit or an Unscheduled Visit within the Month 1 visit window will be used as Baseline in a sensitivity analysis. Changes from Baseline at Month 12, Month 60 and the Final Visit will also be summarized.

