- Years 9 and 10 will only include the LNG20 16-35 year old enrollment group
- IUS expulsion rates at 1 year, 2 years, 3 years, 4 years, 5 years, 6 years, 7 years, 8 years, 9 years and 10 years
 - Years 6, 7 and 8 will only include LNG20 subjects
 - Years 9 and 10 will only include the LNG20 16-35 year old enrollment group
- IUS safety-related removal rates at 1 year, 2 years, 3 years, 4 years, 5 years, 6 years, 7 years, 8 years, 9 years and 10 years
 - Years 6, 7 and 8 will only include LNG20 subjects
 - Years 9 and 10 will only include the LNG20 16-35 year old enrollment group
- Vaginal bleeding patterns during IUS use
- Dysmenorrhea during IUS use
- Hemoglobin over the duration of IUS use
- Adverse events
- Pregnancy outcomes
- Fertility rates one year following removal of the IUS
- Occurrence of menses after IUS discontinuation
- Plasma levonorgestrel levels over the duration of IUS use
- Analysis of an appropriate sampling of IUSs that are removed or expelled during the study

Other secondary outcomes that will be assessed for LNG20 will include:

- Plasma levonorgestrel levels over the first 14 days following LNG20 removal after Month 121
- Endometrial thickness at 1, 5 and 10 years of LNG20 use as compared to baseline

Duration of Subject Participation:	LNG20 16-35 year old enrollment group: up to 11 years, 1 month (approximately 133 months) LNG20 36-45 year old enrollment group: up to 9 years, 1 month (approximately 109 months) Mirena group: up to 6 years, 1 month (approximately 73 months)
Duration of Study Center Participation:	Up to 14.7 years from start of study enrollment assuming 3 months for study start-up activities, an enrollment period up to 3 years, up to 10 years and 1 month subject treatment, 1 year pregnancy follow-up and 3 months post-monitoring/query resolution.

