6.4 Post-Insertion Study Follow-Up Visits

Post-insertion study follow-up evaluations will occur at Months 1, 3, 6, 12, 18, 24, 30, 36, 42, 48, 54, 60, 66, 72, 78, 84, 90, 96, 102, 108, 114 and 120 (LNG20 36-45 year old group only through Month 90 and Mirena subjects only through Month 54). The visits should occur within 14 days before or after the expected calendar visit date (within 7 days for the Month 1 and 3 visits).

- Diaries
 - Collect diaries and review for appropriate completion.
 - Confirm menstrual bleeding and cramping information is entered correctly (Months 1, 3, 6, 12, 18, and 24 only)
 - Confirm other contraception use is entered correctly

- Confirm compliance with study IUS by reviewing other contraception method(s) documented in diaries.
- The IUS would be considered her primary method of contraception if no regular use of other contraception is indicated on the diaries
 - Dispense additional diaries as needed
- Medical review
 - Review of adverse events or changes in medical history
 - Review of concomitant medications
 - Complete Bleeding/Cramping Form
 - All subjects: Months 30, 36, 42, 48 and 54
 - All LNG20 subjects: also Months 60, 66, 72, 78, 84
 - LNG20 16-35 year old enrollment group: also Months 90, 96, 102, 108, 114 and 120
 - Inquire about change in sexual partner
- Collection of blood sample for
 - Hemoglobin
 - All subjects: Month 12
 - All LNG20 subjects: also Month 60
 - LNG20 16-35 year old enrollment group only: Also Month 120
 - Plasma levonorgestrel
 - All subjects: Months 36, 42, 48 and 54
 - LNG20 subjects enrolled prior to 31May2011:
 - LNG20 16-35 year old enrollment group: also Months 60, 72, 84, 96, 108 and 120
 - LNG20 36-45 year old enrollment group: also Months 60, 72 and 84
- Physical examination and testing
 - High sensitivity urine pregnancy test (if positive, see Sections 7.4 and 7.5)
 - Weight and blood pressure (both must be measured at each visit)
 - Breast exam
 - All subjects: Months 12, 24, 36 and 48
 - All LNG20 subjects: also Months 60, 72 and 84

- LNG20 16-35 year old enrollment group: also Months 96, 108 and 120
- Any clinically indicated physical examination
- Clinically verify presence of IUS by palpation or direct visualization of strings (for missing strings management see Section 6.14 and Appendix C)
- Pelvic exam
 - All subjects: Months 12, 24, 36 and 48
 - All LNG20 subjects: also Months 60, 72, 84
 - LNG20 16-35 year old enrollment group: also Months 96, 108 and 120

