6.6 Study Treatment Completion/Early Discontinuation

Study treatment completion will occur at the end of 60 months of Mirena IUS use, 96 months of LNG20 IUS use for the 36-45 year old enrollment group or 121 months of LNG20 IUS use in the 16-35 year old enrollment group. The visit should occur within 14 days before or after the completion of 60 months of Mirena use or 96 months for the LNG20 IUS 36-45 year old enrollment group; the visit should occur within 7 days before or after the completion of 121 months of use for the LNG20 IUS 16-35 year old enrollment group. The same assessments should be performed if Early Discontinuation occurs.

- Inquire about last intercourse; if possible, any subjects who had intercourse (with intravaginal ejaculation) within the preceding 24 hours should have the Discontinuation Visit rescheduled to a time more than 24 hours from intercourse.
- Collect diaries and review for appropriate completion. Confirm compliance with study IUS by reviewing contraception method(s) documented in diaries since the last scheduled study contact.
- Complete Bleeding/Cramping Form (**only if discontinuation after Month 24**)
 - Include only information since the last time the form was completed;
 - If the last study visit or contact (phone or email) was more than 3 months ago, only include the information for last 3 months;

- If Early Discontinuation is during Months 25- 27, include only information beginning with Month 25
- Review of adverse events or changes in medical history
- Review of concomitant medications
- Inquire about change in sexual partner
- Collection of blood sample for:
 - Hemoglobin if not done within the last 3 months
 - Plasma levonorgestrel (only if after Month 36 or for subjects participating in the PK Substudy) if not done within the last 3 months
- High sensitivity urine pregnancy test (if positive, see Sections 7.4 and 7.5)
- Weight and blood pressure
- Breast and pelvic exam (if not performed within the last 3 months)
- Any clinically indicated physical examination
- Pap test if indicated, see section 6.11
- STD testing:
 - Chlamydia testing for all subjects 25 years old or younger who have not had any testing within the last 6 months
 - Chlamydia and gonorrhea testing for any subject following a change in sexual partner since the last study visit. In addition HIV and any other appropriate STD testing should be performed as recommended by the CDC

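### For LNG20 users aged 16-35, SAP 11.13.1 gives the Month 120 hemoglobin neither a summary row nor a link to the Final Visit, so read literally the 10-year values appear only in listings

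*SAP*

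**What the plan says.** The protocol synopsis lists among its other secondary outcomes "Hemoglobin over the duration of IUS use". Protocol 6.4 schedules the draw at Month 12 for everyone, then "All LNG20 subjects: also Month 60", then "LNG20 16-35 year old enrollment group only: Also Month 120".

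Protocol 6.6 sets treatment completion at "121 months of LNG20 IUS use in the 16-35 year old enrollment group". At that visit, and at early discontinuation, the blood sample is qualified: "Hemoglobin if not done within the last 3 months".

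SAP 11.13.1 states: "Hemoglobin will be summarized using descriptive statistics at Baseline, Month 12, Month 60 and the Final Visit". It then says "Final Visit is defined as either the early discontinuation or study treatment completion visit", and for changes, "Changes from Baseline at Month 12, Month 60 and the Final Visit will also be summarized". The only special handling in that section concerns a missing baseline value. SAP 5.3 does not impute missing data unless a section says otherwise, and SAP 1 puts the SAP above the protocol where their statistical analyses differ.

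**The concern.** The Month 120 draw is the only scheduled 10-year hemoglobin measurement, and the summary has no row for it. The row that looks like its natural home, Final Visit, is tied to a visit at which most completers in this group will have no hemoglobin drawn.

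A reader of the table would take Final Visit to be the end-of-treatment result. For LNG20 16-35 it would instead describe women who stopped early, at any time from the first weeks to nearly ten years, for reasons that can include bleeding, which bears directly on hemoglobin. The same label would mean something different in the LNG20 36-45 column. What is at stake is a descriptive secondary outcome at the duration of use that the extended protocol was written to study.

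**Working it through.** The plan states no hemoglobin sample size or precision figure, so there is none to reproduce. The check is the visit arithmetic, followed by the make-up of the Final Visit row.

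**Step 1: is the Month 121 draw skipped?** Inputs:
- Month 120 window: 14 days either side (protocol 6.4)
- Month 121 window: 7 days either side (protocol 6.6)
- one month: 30.4 days (SAP 5.4)

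Results:
- shortest gap: 30.4 − 14 − 7 = 9.4 days
- longest gap: 30.4 + 14 + 7 = 51.4 days
- 3 months: 3 × 30.4 = 91.2 days

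Every in-window completer with a Month 120 hemoglobin is therefore exempt at Month 121.

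**Step 2: does the Month 120 value reach a summary?** It is not one of the four listed time points. It is not taken at the early discontinuation or completion visit. No mapping rule exists, and SAP 5.3 rules out filling the gap by default. It therefore reaches no summary. By contrast, SAP 11.14 does list endometrial thickness at 1, 5 and 10 years.

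**Step 3: how many women?** SAP 4 gives two routes from 1,600 women.
- Stated cumulative discontinuation of 76%: 1,600 × 0.24 = 384 remain, in line with its figure of at least 375.
- Stated annual limits (20%, 19%, 17%, then 16% for seven years) compounded: 0.80 × 0.81 × 0.83 × 0.84^7 = 0.159, so 1,600 × 0.159 ≈ 254 remain.

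The two routes do not agree, so both are kept as a range: 254 to 384 completers, and 1,346 to 1,216 early discontinuers.

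**Step 4: who is in the LNG20 16-35 Final Visit row?** Let m be the share of completers without a Month 120 value (drawn at Month 121 instead) and f the share of early discontinuers with a Final Visit value. Neither is in the documents. I assumed m from 0 to 10% and f from 50% to 100%. Completers' share = (completers × m) / (completers × m + discontinuers × f).
- m = 0: 0%
- m = 10%, f = 50%, compounded rates: 25.4 / (25.4 + 673) ≈ 4%
- m = 10%, f = 50%, stated 76%: 38.4 / (38.4 + 608) ≈ 6%

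If Month 120 counted as the completion value for all completers, their share would run from 254 / 1,600 ≈ 16% (f = 100%) to 384 / (384 + 608) ≈ 39% (f = 50%).

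**Step 5: the other groups.** LNG20 36-45 completers finish at Month 96 and their last scheduled draw is Month 60, so 6.6 requires a draw. Applying the same annual rates (an assumption for this group), 0.80 × 0.81 × 0.83 × 0.84^5 = 0.225, and 150 × 0.225 ≈ 34 completers. They would be about 22% (f = 100%) to 37% (f = 50%) of that column.

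For Mirena, 6.6 would also require a draw at Month 60, since the last scheduled one is Month 12. The Mirena schedule in Appendix A, as it reads in the converted text, marks hemoglobin only at enrollment and Month 12. That table may be damaged, so no Mirena figure is relied on here.

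**The case against.** The strongest reply is that the 3-month rule in protocol 6.6 exists so that a recent value can stand for the completion assessment. On that view the Month 120 value is the completer's Final Visit value and nothing is lost. This is a sensible intention, but the SAP does not state it: the Final Visit is defined by visit, not by the last available value. The objection reduces the defect to an unstated derivation rule. It does not remove it, because a programmer following the text would produce the literal result.

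A reader might infer that the 10-year hemoglobin is never reported. The documents do not support that: SAP 5.1 puts case report form data into subject listings, so Month 120 values would be listed. Protocol 9.8 also foresees descriptive summaries of hemoglobin changes as appropriate, but names no time point.

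A reader might also infer that the Final Visit row is almost only early discontinuers in every column. That fails for LNG20 36-45 and is unsettled for Mirena. Nor does the protocol forbid a Month 121 draw: a woman who missed Month 120 would be drawn then. Both visit windows are worded as targets, so the 9 to 51 day range covers in-window visits only.

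Finally, hemoglobin is one of many descriptive outcomes, and a pooled final-visit row is not in itself an error. Both points stand, and they limit the weight of the concern.

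**Conclusion.** The concern holds for the LNG20 16-35 group, the only group followed to ten years. As written, its 10-year hemoglobin values enter no pre-specified summary of values or changes, and its Final Visit row is 94% to 100% early discontinuers under the assumptions in the working. The number of women affected is about 254 to 384, less any without a Month 120 draw. It should not be quoted simply as the 375 or more in SAP 4, because the annual rates in the same section compound to a lower figure.

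The conclusion rests on in-window visits and on reading the Final Visit definition literally. The Pearl Index does not depend on it, and no formal test is planned in the study. It should be corrected because the result would mislead and the correction is nearly free.

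**What to change.** In SAP 11.13.1, do one of the following:
- add Month 120 (value and change from baseline) as a time point for LNG20 16-35; or
- state that a hemoglobin obtained within 3 months before treatment completion counts as the completion value.

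In either case, show treatment completers separately from early discontinuers instead of pooling them under Final Visit. Breaking early discontinuation down further by year of use is a matter of layout and is not needed. While editing, check the Mirena schedule in Appendix A against protocol 6.6, so that it is clear whether Mirena completers have a Month 60 hemoglobin.

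The cost is SAP wording and extra table rows. The samples are already planned, and no visit changes.
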